4.4.2.2 PARTICIPANT CLASSIFICATION FOR ANTIBODIES AGAINST rHuPH20

Table 7 below gives an overview of how the anti-rHuPH20 antibody (rHuPH20 Ab) participant classification will be derived, starting from the participant baseline rHuPH20 Ab sample status.

Table 7: Participant classification for antibodies against rHuPH20

Participant anti-rHuPH20 Ab classification	Highest ^c post-baseline sample status				
	rHuPH20 Ab negative	rHuPH20 Ab positive (missing titer ^a)	rHuPH20 Ab positive (negative titer ^b or numeric titer value)		rHuPH20 Ab not evaluable
Baseline rHuPH20 Ab sample status					
rHuPH20 Ab negative	rHuPH20 Ab negative	Treatment-Induced rHuPH20 Ab	Treatment-Induced rHuPH20 Ab		rHuPH20 Ab unevaluable
rHuPH20 Ab positive (missing titer^a)	Treatment-Unaffected rHuPH20 Ab	rHuPH20 Ab unevaluable	rHuPH20 Ab unevaluable		rHuPH20 Ab unevaluable
rHuPH20 Ab positive (negative titer^b or numeric titer value)	Treatment-Unaffected rHuPH20 Ab	rHuPH20 Ab unevaluable	titer < 4 x baseline titer: Treatment-Unaffected rHuPH20 Ab	titer ≥ 4x baseline titer: Treatment-Boosted rHuPH20 Ab	rHuPH20 Ab unevaluable
rHuPH20 Ab not evaluable	rHuPH20 Ab unevaluable	rHuPH20 Ab unevaluable	rHuPH20 Ab unevaluable		rHuPH20 Ab unevaluable

^a Samples with missing titer have as reported rHuPH20 Ab result 'positive immunodepletion' or 'positive titer';

^b Results reported as 'negative titer', i.e. titer value <5 will be set to value of 5;

^c Highest sample status, with order: (from low to high): rHuPH20 Ab *unevaluable*, rHuPH20 Ab negative, rHuPH20 Ab positive (missing titer/positive immunodepletion), rHuPH20 Ab positive with titer ≤ 5 ('negative titer' as reported rHuPH20 Ab result, titer value set to 5), rHuPH20 Ab positive with titer >5 (i.e. positive titer and selecting the sample with highest titer)

rHuPH20 Ab evaluable participant = participant classified as any of following categories: rHuPH20 Ab negative, treatment-unaffected rHuPH20 Ab, treatment-induced rHuPH20 Ab, treatment-boosted rHuPH20 Ab. The first 2 categories are classified as 'rHuPH20 Ab negative', the latter 2 as 'rHuPH20 Ab positive'.

rHuPH20 Ab *unevaluable* participant = participant classified as rHuPH20 Ab *unevaluable* or with missing baseline rHuPH20 Ab sample or without post-baseline rHuPH20 Ab samples

Anti-rHuPH20 Ab incidence = percentage of participants with treatment-induced or treatment-boosted rHuPH20 Ab s (denominator: number of evaluable participants).

Anti-rHuPH20 Ab prevalence = percentage of participants with treatment-unaffected rHuPH20 Ab, treatment-induced rHuPH20 Ab or treatment-boosted rHuPH20 Ab (denominator: number of evaluable participants).

	Statistical Analysis Plan	
ARGX-113-1904	Final analysis	Final 2.0 of 22NOV2023

4.4.2.3 PARTICIPANT CLASSIFICATION FOR NAB AGAINST EFGARTIGIMOD

All ADA confirmed positive samples will also be evaluated in the NAb assay. All samples that were not analyzed in the NAb assay (i.e. the ADA negatives) are per default NAb negative. Also, if a NAb sample is not reported, the NAb sample status is NAb unevaluable.

For NAb against efgartigimod, all samples evaluated in the NAb assay will be scored as NAb positive, NAb negative or NAb unevaluable by the laboratory. Based on these results, the participants will be categorized based on their baseline and post-baseline sample status as detailed in Table 8.

Table 8: Participant classification for NAb against Efgartigimod

Participant NAb classification	Highest ^a post-baseline NAb sample status		
	NAb negative	NAb positive	NAb not evaluable
Baseline NAb sample status			
NAb negative	baseline neg – post-baseline neg	baseline neg – post-baseline pos	NAb unevaluable
NAb positive	baseline pos – post-baseline neg	baseline pos – post-baseline pos	NAb unevaluable
NAb not evaluable	NAb unevaluable	NAb unevaluable	NAb unevaluable

^a Highest sample status in order: (from low to high): NAb unevaluable, NAb negative, NAb positive

NAb unevaluable participant = participant classified as NAb unevaluable or with missing baseline NAb sample or without post-baseline NAb samples.

NAb incidence = percentage of participants with participant classification ‘baseline neg – post-baseline pos’ and ‘baseline pos – post-baseline pos’ (denominator: number of evaluable participants).

NAb prevalence = percentage of participants with participant classification ‘baseline neg – post-baseline pos’, ‘baseline pos – post-baseline pos’ or ‘baseline pos – post-baseline neg’ (denominator: number of evaluable participants).

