Per parameter and analysis window, the value closest to the target ADYP will be used in analysis tables, other values will only be listed. If more than one value is located at the same distance from the target, then the latest in time will be selected. The value latest in time will be identified using, in order of preference, the assessment time, the visit label or the group identifier (if applicable). For immunogenicity assessments, missing values resulting in an unavailable ADA/NAb status are given the lowest priority when the selection is made. For other assessments, missing values are removed before the selection is made.

Partially missing assessment dates disabling allocation to analysis windows will not be imputed and thus these assessments will not be considered in the per-timepoint analysis. Note that these assessments are included in analyses on worst-case.

	Statistical Analysis Plan	
ARGX-113-1904	Final analysis	Final 2.0 of 22NOV2023

As the schedule of assessments is dependent of CR and consequently varies between participants, data might get spread over time for the 4-weekly visits after CR. Therefore some visit windows will be changed for some parameters:

1. For ABQOL and EQ-5D-5L
 - Week 14 (wide range): from ADYP=96 until ADYP=123
 - Week 30 (wide range): from ADYP= 124 until ADYP=end of treatment phase
 - Additional visit window: Endpoint: last record post baseline.
2. For GTI
 - Week 14 (wide range): from ADYP=61 until ADYP=137 with target on ADYP=99
 - Week 30 (wide range): from ADYP=173 until ADYP= end of treatment phase with target on ADYP=211
 - Other assessments will be allocated as in table 3 but will not be presented in the tables (only in listings).
 - Additional visit window: Overall: last record post baseline.
3. For ECG
 - Week 11 (wide range): from ADYP=75 until ADYP=102

The same rules for record selection as for the regular visit windows will be applied in case of more records occur in the same window.

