4.4.2.4 PARTICIPANT CLASSIFICATION FOR NAB AGAINST rHUPH20

All rHuPH20 Ab confirmed positive samples will also be evaluated in the NAb assay against rHuPH20. All samples that were not analyzed in the NAb assay (i.e. the rHuPH20 Ab negatives) are per default NAb negative. Also, if a NAb sample is not reported, the NAb sample status is NAb unevaluable. NAb against rHuPH20 will be evaluated using a screening assay followed by titer analysis (ie, a 2-tiered approach). For NAb against rHuPH20, all samples evaluated in this NAb screening assay will be scored as NAb negative or NAb positive by the laboratory. In case the sample is NAb positive, a titration assay will occur and the sample will be reported as 'negative titer',

'positive titer' or by an actual titer value. Based on these results, the participants will be categorized based on their baseline and post-baseline sample status as detailed in following Table 9.

A 3-tiered approach, including an additional NAb confirmatory assay to determine the specificity of the response, will be implemented as a post-hoc analysis. This analysis will be described in an addendum to this SAP or the ISI (Integrated Summary of Immunogenicity) SAP.

Table 9: Participant classification for NAb against rHuPH20

Participant rHuPH20 NAb classification	Highest ^c post baseline sample status				
	rHuPH20 NAb negative	rHuPH20 NAb positive (missing titer ^a)	rHuPH20 NAb positive (negative titer ^b or numeric titer value)		rHuPH20 NAb not evaluable
Baseline rHuPH20 NAb sample status					
rHuPH20 NAb negative	rHuPH20 NAb negative	Treatment Induced rHuPH20 NAb	Treatment Induced rHuPH20 NAb		rHuPH20 NAb unevaluable
rHuPH20 NAb positive (missing titer^a)	Treatment Unaffected rHuPH20 NAb	rHuPH20 NAb unevaluable	rHuPH20 NAb unevaluable		rHuPH20 NAb unevaluable
rHuPH20 NAb positive (negative titer^b or numeric titer value)	Treatment Unaffected rHuPH20 NAb	rHuPH20 NAb unevaluable	titer < 4 x baseline titer: Treatment Unaffected rHuPH20 NAb	titer ≥ 4x baseline titer: Treatment Boosted rHuPH20 NAb	rHuPH20 NAb unevaluable
rHuPH20 NAb not evaluable	rHuPH20 NAb unevaluable	rHuPH20 NAb unevaluable	rHuPH20 NAb unevaluable		rHuPH20 NAb unevaluable

^a Samples with missing titer have as reported rHuPH20 NAb result 'positive screen' or 'positive titer';
^b Results reported as 'negative titer', i.e. titer value <100 will be set to value of 100;

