4.4.3 Presentation of results

Analyses will be done for ADA against efgartigimod and antibodies against rHuPH20.

Frequency tabulations (number and percentages) will be provided with ADA or rHuPH20 Ab negative/positive/unevaluable samples per analysis visit. These tables will be presented by ADA or rHuPH20 Ab participant category.

Frequency tabulations (number and percentages) will be provided by treatment on:

- Participants per ADA or rHuPH20 Ab participant classification
- Prevalence and incidence of ADA or rHuPH20 Ab
- ADA or rHuPH20 Ab unevaluable participants
- ADA or rHuPH20 Ab baseline positive/negative samples

For details on the definitions, see the above section 4.4.2.1. and 4.4.2.2.

The above frequency tabulations will be repeated for NAb assay using the definitions as defined in section 4.4.2.3. and 4.4.2.4.

In addition, a frequency tabulation (number and percentages) will be provided for:

- NAb against efgartigimod positive participants within the ADA participant classification (Treatment-unaffected ADA, Treatment-induced ADA, Treatment-boosted ADA, ADA Negative, ADA Unevaluable)
- NAb against rHuPH20 Ab positive participants within the rHuPH20 Ab participant classification
- rHuPH20 Ab positive participants within efgartigimod ADA participant classification

Correlation tables by ADA and NAb participant classification against efgartigimod and by rHuPH20 Ab will be provided for the following parameters for PV and PF participants combined:

	Statistical Analysis Plan	
ARGX-113-1904	Final analysis	Final 2.0 of 22NOV2023

- Mean (SD) drug concentration over time
- Mean (SE) percent change from baseline in total IgG
- Overall Treatment-Emergent Adverse Events by MedDRA System Organ Class and Preferred Term by Overall Anti-Drug Antibodies Participant Classification
- Overall Serious Treatment-Emergent Adverse Events by MedDRA System Organ Class and Preferred Term by Overall Anti-Drug Antibodies Participant Classification
- Overall Injection-related reactions by Overall Anti-Drug Antibodies Participant Classification
- Overall Injection site reactions by Overall Anti-Drug Antibodies Participant Classification
- Proportion of participants with CRmin within 30 weeks*

* Difference in proportion responders between each of the 4 categories versus ADA Negative, NAb baseline neg – post-baseline neg and rHuPH20 Ab Negative, including 95% exact confidence interval will be calculated.

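### SAP 4.4.2.3 and 4.4.2.4 let an untested antibody-negative sample outrank a missing NAb result, so some antibody-positive participants of unknown neutralising status are counted as evaluable NAb negatives

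*SAP*

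**What the plan says.** SAP 4.4.2.3 sets out four rules for NAb against efgartigimod.

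- Entry to the assay: "All ADA confirmed positive samples will also be evaluated in the NAb assay".
- Samples that do not enter it: "All samples that were not analyzed in the NAb assay (i.e. the ADA negatives) are per default NAb negative".
- Samples with no result: "Also, if a NAb sample is not reported, the NAb sample status is NAb unevaluable".
- Roll-up to the participant (Table 8, footnote a): "Highest sample status in order: (from low to high): NAb unevaluable, NAb negative, NAb positive".

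The participant-level definition of unevaluable is: "NAb unevaluable participant = participant classified as NAb unevaluable or with missing baseline NAb sample or without post-baseline NAb samples". Incidence and prevalence both use evaluable participants as the denominator.

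SAP 4.4.2.4 follows the same pattern for rHuPH20. Its default reads "i.e. the rHuPH20 Ab negatives) are per default NAb negative", and Table 9, footnote c, again puts unevaluable below negative. SAP 2.2.4 points the same way when several samples fall in one visit window: "For immunogenicity assessments, missing values resulting in an unavailable ADA/NAb status are given the lowest priority when the selection is made".

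SAP 4.4.3 then uses the classes. It tabulates "NAb against efgartigimod positive participants within the ADA participant classification", and it presents drug concentration, IgG change, adverse events and CRmin by efgartigimod NAb class. The class that is negative both at baseline and post-baseline (neg–neg below) is the reference for the CRmin differences.

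**The concern.** A default negative is not a NAb measurement. It is reasonable for a visit at which no antibody was found, but it says nothing about whether antibody found at another visit neutralises. Because negative outranks unevaluable, one such visit overrides missing NAb results on the only samples that could have been NAb positive.

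The SAP handles the neighbouring problem differently. In Tables 6 and 7, a confirmed-positive sample with a missing titer ranks above a negative sample, so a negative visit cannot hide it. In Table 8 the missing NAb result ranks below the default negative.

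At stake are NAb incidence and prevalence, which the plan means to base on evaluable participants, and the make-up of the efgartigimod neg–neg class.

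**Working it through.** No stated figure can be reproduced here, so the check applies the rules to sample patterns.

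**Inputs.** The four rules and Table 8 from SAP 4.4.2.3; Table 6 from SAP 4.4.2.1; 213 participants randomized 2:1 from SAP 1.3.

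**Step 1: apply the rules.** ADA-negative sample = NAb negative. ADA-positive sample without a NAb result = unevaluable. Take the highest post-baseline status, then read Table 8.

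| Baseline sample | Post-baseline samples | Table 8 class |
|---|---|---|
| ADA neg | ADA neg; ADA pos, no NAb; ADA pos, no NAb | neg–neg, evaluable |
| ADA neg | three ADA pos, no NAb | unevaluable |
| ADA pos, no NAb | ADA neg; ADA pos, no NAb | unevaluable |
| ADA neg | three ADA neg | neg–neg |
| ADA neg | ADA neg; ADA pos, no NAb; ADA pos, NAb pos | neg–pos |
| ADA pos, NAb neg | ADA neg; ADA pos, no NAb | neg–neg, evaluable |
| ADA pos, NAb pos | ADA neg; ADA pos, no NAb | pos–neg, evaluable |

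Rows 1, 6 and 7 show the fault: post-baseline neutralising status is unknown but is reported as negative. Table 6 classes the row 1 participant as having treatment-induced ADA. Rows 2 and 3 are correctly unevaluable.

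**Step 2: conditions.** All three are needed: an evaluable baseline NAb status; at least one antibody-negative post-baseline sample; and no NAb result on any antibody-positive post-baseline sample.

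Take an ADA-negative baseline and k post-baseline samples, each either ADA negative or ADA positive without a NAb result, with at least one positive. There are 2^k − 1 such patterns, and only the all-positive one is unevaluable. That leaves 6 of 7 classed negative for k = 3 and 254 of 255 for k = 8. These are counts of patterns, not probabilities.

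**Step 3: direction.** Let N be the participants now counted as evaluable, a the NAb positives and m the affected participants.

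- Incidence as written: a/N.
- With the m excluded: a/(N − m), which is higher.
- If all m were NAb positive: (a + m)/N, higher still.

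Rows 1 and 6 lower both incidence and prevalence. Row 7 lowers incidence only, since its class already counts towards prevalence.

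**Step 4: illustration.** N = 213 × 2/3 = 142 assumes every efgartigimod participant is evaluable. The values of a and m are also assumptions; the documents give neither.

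| a | m | As written a/142 | Excluded a/(142 − m) | All positive (a + m)/142 |
|---|---|---|---|---|
| 3 | 1 | 2.11% | 2.13% | 2.82% |
| 3 | 10 | 2.11% | 2.27% | 9.15% |
| 6 | 1 | 4.23% | 4.26% | 4.93% |
| 6 | 5 | 4.23% | 4.38% | 7.75% |
| 6 | 10 | 4.23% | 4.55% | 11.27% |
| 12 | 1 | 8.45% | 8.51% | 9.15% |
| 12 | 10 | 8.45% | 9.09% | 15.49% |

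Excluding the unknowns changes the estimate little. What the plan hides is mainly the uncertainty in the last column.

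**The case against.** The strongest reply is that the trigger may be rare and the outputs are transparent. Every confirmed-positive sample is sent to the NAb assay, and a participant is affected only if all antibody-positive post-baseline samples lack a result. SAP 4.4.1 mentions insufficient volume or quality only for titration. The default is openly stated, sample-level NAb status is tabulated by visit within participant class, and all results are listed, so a careful reader could find unevaluable samples inside the neg–neg class. That class also pools ADA-negative with ADA-positive, NAb-negative participants by design.

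Most of this stands as a limit on size. It does not remove the error: SAP 4.4.2.3 itself lets the laboratory score a sample as unevaluable, and the summary incidence still counts the participant as a known negative. Nor does the clause on participants without post-baseline NAb samples rescue the text. If it meant no sample run in the assay, every ADA-negative participant would become unevaluable, contrary to the default rule.

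A reader might infer three stronger things that the documents do not support.

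- **That the unevaluable class is almost unreachable for ADA-positive participants.** Rows 2 and 3 above reach it. How often treatment-induced ADA is preceded by an ADA-negative sample is a matter of kinetics on which the documents are silent.
- **That the NAb share among ADA-positive participants is understated by the fraction with missing results.** Moving participants from negative to unevaluable leaves the number of NAb positives unchanged. The percentage moves only if the denominator changes too. SAP 4.4.3 sets no specific denominator for that table; the general rule in SAP 2.4.1 is the analysis set per treatment, less missing values.
- **That the rHuPH20 version distorts the PK, IgG, adverse-event or CRmin tables.** SAP 4.4.3 builds those on efgartigimod ADA, efgartigimod NAb and rHuPH20 antibody classes, not on rHuPH20 NAb.

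**Conclusion.** The classification rule is wrong as written for participants meeting the three conditions in step 2, and no other section corrects it. It biases NAb incidence downward for efgartigimod and rHuPH20, and prevalence downward where the baseline is NAb negative. For efgartigimod only, it also puts participants of unknown neutralising status into the neg–neg class used in the correlation tables and as the CRmin reference.

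The number affected cannot be derived from the documents and may be small; the percentages above rest on assumed counts. The outputs are descriptive, and neither the primary analysis nor the fixed-sequence tests are touched. This is a minor point, worth correcting because the remedy is simple.

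**What to change.** Add one rule to SAP 4.4.2.3 and 4.4.2.4. For a participant with at least one antibody-confirmed-positive post-baseline sample, derive post-baseline NAb status from the antibody-positive samples only:

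- positive if any is NAb positive;
- negative if at least one is NAb negative and none is positive;
- unevaluable if none has a NAb result.

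Apply the default negative at participant level only when all evaluable post-baseline samples are antibody negative. In the table of NAb positives within ADA class, show the unevaluable count separately.

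Under this rule rows 1, 6 and 7 become unevaluable and the other rows keep their class. A stricter version would make a participant without a NAb-positive sample unevaluable if any antibody-positive sample lacked a result. The rule above still lets a measured negative stand, so the SAP should say which is meant.

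The cost is a short change to the SAP text and the derivation program, and a few participants moving to unevaluable. One side effect is that a baseline NAb-positive participant (row 7) would also leave the prevalence count under Table 8, so that cell should be footnoted.

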4.4 IMMUNOGENICITY

4.4.1 *Available data*

Blood samples will be collected for the determination of anti-drug antibodies (ADA) to efgartigimod (in serum samples) and antibodies against rHuPH20 (in plasma samples) at the time points indicated in the schedule of assessments (see section 9.5).

Immunogenicity samples are analyzed in a 3-tiered approach:

- All samples are evaluated in the ADA screening assay and are scored as ADA screening positive or negative.
- If a sample scored positive in the ADA screening assay, it is further evaluated in the confirmatory assay and is scored confirmed positive (positive immunodepletion) or confirmed negative (negative immunodepletion).
- If a sample is scored as confirmed positive, the samples are further characterized in the ADA titration assay (to determine titer) and are also further analyzed in the Nab assay to confirm neutralizing activity. For Nab against efgartigimod, a screening assay is performed and results will be reported as negative or positive. For Nab against rHuPH20, the screening Nab assay is followed by a titer Nab assay in case the sample screened positive.

[figure not shown]
If available, a titer result will be reported for the ADA confirmed positive samples. However, a titer result is not always available:

- In case the ADA confirmed positive sample could not be run in the titration assay (e.g., due to insufficient sample volume/quality to perform the titer analysis), the result will be described as ‘positive immuno-depletion’ and the sample should be considered as ADA positive.
- If a sample is negative in the titration assay, it will be reported as ‘negative titer’ but it should be considered as ADA positive since it was confirmed positive in the second tier.
- If a sample could not be analyzed or reported as ‘positive screen’, the ADA sample status is ADA unevaluable.

An overview of this 3-tiered approach and all possible ADA sample results that will be reported by the laboratory is given below. From these reported ADA sample

results a final ADA sample status needs to be derived during the statistical analysis, as presented in the final column ('Final ADA Outcome'):

Figure 1: ADA sample status

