4.4.2 Derivation rules

4.4.2.1 PARTICIPANT CLASSIFICATION FOR ADA AGAINST EFGARTIGIMOD

Table 6 below gives an overview of how the ADA participant classification will be derived, starting from the participant baseline ADA sample status.

Table 6: Participant classification for ADA against Efgartigimod

Participant ADA classification	Highest ^c post-baseline sample status				
	ADA negative	ADA positive (missing titer ^a)	ADA positive (negative titer ^b or numeric titer value)		ADA not evaluable
Baseline ADA sample status					
ADA negative	ADA negative	Treatment-Induced ADA	Treatment-Induced ADA		ADA unevaluable
ADA positive (missing titer^a)	Treatment-Unaffected ADA	ADA unevaluable	ADA unevaluable		ADA unevaluable
ADA positive (negative titer^b or numeric titer value)	Treatment-Unaffected ADA	ADA unevaluable	titer < 4 x baseline titer: Treatment-Unaffected ADA	titer ≥ 4x baseline titer: Treatment-Boosted ADA	ADA unevaluable
ADA not evaluable	ADA unevaluable	ADA unevaluable	ADA unevaluable		ADA unevaluable

^a Samples with missing titer have as reported ADA result 'positive immunodepletion' or 'positive titer';

^b Results reported as 'negative titer', i.e. titer value <1 will be set to value of 1;

^c Highest sample status, with order: (from low to high): ADA unevaluable, ADA negative, ADA positive (missing titer /positive immunodepletion), ADA positive with titer ≤ 1 ('negative titer' as reported ADA result, titer value set to 1), ADA positive with titer >1 (i.e. positive titer and selecting the sample with highest titer)

ADA evaluable participant = participant classified as any of following categories: ADA negative, treatment-unaffected ADA, treatment-induced ADA, treatment-boosted ADA. The first 2 categories are classified as 'ADA negative', the latter 2 as 'ADA positive'.

ADA unevaluable participant = participant classified as ADA unevaluable or with missing baseline ADA sample or without post-baseline ADA samples.

Note: Fourfold difference in titer values is considered significant in case a twofold serial dilution is applied (= 2 times the dilution factor) (reference to Shankar et al., 2014).

ADA incidence = percentage of participants with treatment-induced or treatment-boosted ADAs (denominator: number of evaluable participants).

ADA prevalence = percentage of participants with treatment-unaffected ADA, treatment-induced ADA or treatment-boosted ADA (denominator: number of evaluable participants).

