^c Highest sample status, with order: (from low to high): rHuPH20 NAb unevaluable, rHuPH20 NAb negative, rHuPH20 NAb positive (missing titer), rHuPH20 NAb positive with titer <100 ('negative titer' as reported NAb result, titer value set to 100), rHuPH20 NAb positive (i.e. actual titer value and selecting the sample with highest titer).

rHuPH20 NAb evaluable participant = participant classified as any of following categories: rHuPH20 NAb negative, treatment-unaffected rHuPH20 NAb, treatment-induced rHuPH20 NAb, treatment-boosted rHuPH20 NAb. The first 2 categories are classified as 'rHuPH20 NAb negative', the latter 2 as 'rHuPH20 NAb positive'.

	
Statistical Analysis Plan
	

ARGX-113-1904
	
Final analysis
	
Final 2.0 of 22NOV2023

rHuPH20 NAb unevaluable participant = participant classified as rHuPH20 NAb unevaluable or with missing baseline rHuPH20 NAb sample or without post-baseline rHuPH20 NAb samples

NAb incidence = percentage of participants with participant classification ‘treatment-induced rHuPH20 NAb’ or treatment-boosted rHuPH20 NAb’ (denominator: number of evaluable participants).

NAb prevalence = percentage of participants with participant classification ‘treatment-unaffected rHuPH20 NAb’, ‘treatment-induced rHuPH20 NAb’ or ‘treatment-boosted rHuPH20 NAb’ (denominator: number of evaluable participants).

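### Incidence of neutralizing antibodies (NAb) against efgartigimod counts participants who were NAb-positive at baseline and stayed positive, unlike the SAP's other three antibody incidence definitions

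*SAP*

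**What the plan says.** SAP 4.4.2.3 classifies each participant by NAb status at baseline and highest NAb status after baseline. Its incidence line, which begins "NAb incidence = percentage of participants with participant classification", names two classes: "NAb incidence = percentage of participants with participant classification ‘baseline neg – post-baseline pos’ and ‘baseline pos – post-baseline pos", over all evaluable participants. Prevalence adds one further class: "NAb prevalence = percentage of participants with participant classification ‘baseline neg – post-baseline pos’, ‘baseline pos – post-baseline pos’ or ‘baseline pos – post-baseline neg".

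The other three incidence definitions in the same section leave out participants whose antibody was present at baseline and did not rise:

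- SAP 4.4.2.1: "ADA incidence = percentage of participants with treatment-induced or treatment-boosted ADAs (denominator: number of evaluable participants"
- SAP 4.4.2.2: "Anti-rHuPH20 Ab incidence = percentage of participants with treatment-induced or treatment-boosted rHuPH20 Ab s (denominator: number of evaluable participants"
- SAP 4.4.2.4: "NAb incidence = percentage of participants with participant classification ‘treatment-induced rHuPH20 NAb’ or treatment-boosted rHuPH20 NAb"

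The assays differ. SAP 4.4.1 states: "For Nab against efgartigimod, a screening assay is performed and results will be reported as negative or positive". The ADA assay and the rHuPH20 NAb assay can both yield a titer.

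SAP 2.1.1 places immunogenicity on the safety analysis set. SAP 4.4.3 tabulates classification, prevalence and incidence by treatment and repeats those tables for NAb. The planned output is Table 14.2.4.1.4. SAP 6.1, which lists departures from the protocol, does not mention this definition.

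**The concern.** Incidence should describe antibody that appears or rises after treatment starts. A participant who is NAb-positive before the first dose and simply stays positive belongs in prevalence, yet this definition also counts that person as incident.

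Persistent reactivity of this kind cannot have been caused by the trial drug, since the baseline sample is taken before dosing. Protocol exclusion criterion 19 also bars anyone dosed in an earlier efgartigimod trial. A persistently positive placebo participant, who receives no efgartigimod at all, would still be reported as an incident anti-efgartigimod NAb case.

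The rule also sits awkwardly beside the ADA rule. A participant with treatment-unaffected ADA is grouped as ADA negative under SAP 4.4.2.1. If the same participant's samples are NAb-positive at both times, the participant is an incident NAb case under SAP 4.4.2.3. A reader comparing the incidence rows would assume that they share one meaning, and they do not.

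**Working it through.** The plan states no numerical figure for NAb incidence, so there is nothing to reproduce. The check has two parts: setting the definitions side by side, and working out how much the extra class adds.

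**Definitions**

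| Antibody | Counted as incident | Positive at baseline, not raised |
|---|---|---|
| ADA to efgartigimod (4.4.2.1) | induced, boosted | prevalence only |
| Antibody to rHuPH20 (4.4.2.2) | induced, boosted | prevalence only |
| NAb to rHuPH20 (4.4.2.4) | induced, boosted | prevalence only |
| NAb to efgartigimod (4.4.2.3) | neg–pos, pos–pos | incidence and prevalence if still positive |

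Only the last row lets unchanged pre-existing antibody into incidence.

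**Per-participant size.** SAP 1.3 plans about 213 participants at 2:1, which is 213 × 2/3 = 142 on efgartigimod and 71 on placebo. If all are evaluable, one pos–pos participant adds 1/142 = 0.7 points on efgartigimod or 1/71 = 1.4 points on placebo. Fewer evaluable participants would make each step larger.

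SAP 2.4 repeats the descriptive outputs for Japanese participants. The protocol target is 9 with PV plus 1 to 3 with PF, so 10 to 12 in all, or about 7 to 8 on efgartigimod. There, one pos–pos participant adds 1/8 = 12.5 to 1/7 = 14.3 points.

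**General form.** Let b be the share NAb-positive at baseline, s the share of those still positive afterwards, and d the new-onset rate among baseline negatives. None of the three is in the documents; all are assumptions.

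- SAP incidence = (1 − b)d + bs
- Incidence from neg–pos only = (1 − b)d
- Prevalence = (1 − b)d + b

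The inflation is exactly bs. The gap between prevalence and SAP incidence is b(1 − s). When s = 1 that gap vanishes, and the two measures report the same number.

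**Illustration over an assumed range**

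| Arm | d | b | s | SAP incidence | neg–pos only | Prevalence |
|---|---|---|---|---|---|---|
| Efgartigimod | 5% | 1% | 0.5 | 5.45% | 4.95% | 5.95% |
| Efgartigimod | 5% | 2% | 1 | 6.90% | 4.90% | 6.90% |
| Efgartigimod | 5% | 5% | 1 | 9.75% | 4.75% | 9.75% |
| Efgartigimod | 5% | 10% | 1 | 14.50% | 4.50% | 14.50% |
| Placebo | 0% | 1% | 0.5 | 0.50% | 0% | 1.00% |
| Placebo | 0% | 10% | 1 | 10.00% | 0% | 10.00% |

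Over b from 1% to 10% and s from 0.5 to 1, the inflation runs from 0.5 to 10 points. At b = 0 it is zero.

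**The case against.** The strongest defence is that the comparison is not like for like. The efgartigimod NAb assay returns only positive or negative, so an induced-or-boosted rule cannot be applied to it. Counting the whole pos–pos class could then be a cautious upper bound that misses no boosted case. The first part stands: the missing titer explains why this definition cannot simply copy the others. But the SAP does not offer the upper-bound reasoning, and the missing titer does not make unchanged pre-existing antibody incident. It also cannot justify placebo cases, which efgartigimod cannot have boosted.

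A second defence is that nothing is hidden. Table 14.2.4.1.4 shows the classes beside the incidence figure, Table 14.2.4.2.1 crosses NAb positives with ADA class, and Listing 16.2.6.11 gives individual results. This also stands, so a careful reader can rebuild the narrower figure. It limits the harm but does not correct the row labelled incidence, which is the number likely to be quoted.

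A reader might infer more than the documents support:

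- That a named secondary endpoint is misdefined. The protocol endpoint names incidence and prevalence of ADA to efgartigimod and antibodies to rHuPH20. NAb testing follows from confirmed ADA positives and is not itself named.
- That every baseline-positive participant is counted as incident. Those who become negative enter prevalence only.
- That correcting the definition keeps NAb incidence at or below ADA incidence. It does not. A participant who is ADA-positive but NAb-negative at baseline, and later NAb-positive with an ADA titer below four times baseline, is treatment-unaffected for ADA and still an incident NAb case. The evaluable denominators can also differ.

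**Conclusion.** The point holds as an inconsistency of definition. Efgartigimod NAb incidence includes persistent pre-existing reactivity, in both arms, where the SAP's other three incidence measures exclude it, and no reason is given. The inflation equals the pos–pos share of evaluable participants.

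Whether the effect will be visible is unknown. It depends on a baseline NAb rate that the documents do not give, and the 0.5 to 10 point range is only illustrative. The per-participant steps rest on planned numbers and full evaluability.

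The consequence is limited. The figure is descriptive, lies outside the fixed-sequence testing in SAP 4.1.4, and does not feed the tables by NAb class in SAP 4.4.3, which use the participant classes themselves. This is a minor point, worth correcting because the correction is cheap.

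**What to change.** In SAP 4.4.2.3, define efgartigimod NAb incidence as the percentage of evaluable participants who are NAb-negative at baseline and NAb-positive afterwards. In Table 14.2.4.1.4, report the pos–pos class as a separate row, by arm. Add a note that boosted and unaffected cases within it cannot be distinguished because the assay gives no titer. Leave the prevalence definition as it is.

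Do not split the pos–pos class by ADA titer class. That would use total ADA titer as a stand-in for the neutralizing response, which the documents do not support, and it would need an extra rule for participants whose ADA class is unevaluable.

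The cost is one line of definition, one row and one note; the classes are already derived. The downside is that a truly boosted NAb in the pos–pos class is no longer counted as incident, though it stays visible in its own row.
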